Many researchers have reported that, the most critical period for the initiation and progression of occlusal carious lesions is at the time of eruption **(Feather, 2000)**. At the age of 6 years, occlusal surfaces of the permanent first molars are particularly vulnerable to caries development **(Welbury et al., 2004)**. Due to this many preventive strategies using sealants, fluoride varnish, and fluoride gel application was developed in an attempt to stop the caries progression. never less we need to categories the teeth which are at high risk for dental caries, several methods to identify children at increased risk of caries have been developed. These include bacterial and salivary tests in combination with oral hygiene scores and dietary factors. Those complicated prediction tests are considered time consuming and too costly for use in normal dental practice.

On the other hand, Studies on caries risk assessment in children have shown that past caries experience is the best indicator of future caries development ,this Past caries experience is a simple and effective method, as to consider caries in permanent teeth to be a reflective mirror for the past caries experience in primary teeth , **(Topaloglu-Ak & Eden, 2010)**.

This study will investigate whether data of past caries experience of the primary molars of 6-9 years old children can serve as an indicator for caries development in first permanent molars.as the first permanent molars is selected to represent the future caries status of the permanent dentition.

- **Statement of the problem**

One of the main clinical scenarios a pediatric dentist may meet is to extract or do a root canal treatment for the first permanent molars at a young age, which may lead to a serious problem in the occlusion, given that the first permanent molar is the key of occlusion ,many researches have been trying to investigate the underlying cause for the early decay of the first permanent molars including many expensive testes, all aiming to diagnose children at high risk for caries in permanent teeth , another controversy had suggest that caries in primary teeth is not only directly correlated to caries in permanent teeth, but also could be used as risk indicator for caries in first permanent molars, according to(**Topaloglu-Ak & Eden, 2010**), this study suggested the possibility of caries correlation between primary molars and first permanent molars, and that early preventive measures should be applied as early as possible in order to protect the first permanent molar from decay. But is this hypothesis reliable and is there a true correlation between caries in primary molars and first permanent molars?

- **Rationale**

- **Importance of the study trial**

To detect the Relation between caries in primary molars and the development of caries in first permanent molars among Egyptian children.

- **Benefits of practitioners and clinicians**

If this study proves that there is a correlation between caries in primary and permanent molars, practitioners and clinicians will have an indirect benefit. Therefore, they can advise their patients on the importance of early caries-preventive measures.

- **Benefits to patient & Population**

Increase the awareness of importance of implementing oral hygiene and caries-preventive measures among patients and parents.

- **Search Strategy**

The following databases were searched:

- PubMed database.
- Hand searching (Google scholars).

Keywords used in both databases:

- Primary and permanent molars
- Dental caries, Early childhood caries, prevalence of caries
- Children, preschool.

- **Inclusion Criteria**

Included articles should include all of the following criteria:

- Studies applied on normal children.
- Restricted to English language.
- Association between caries in primary and permanent teeth

- **Exclusion criteria**

Articles will be excluded if they include one of the following criteria:

- Other specialties.
- Studies conducted upon adults
- Studies conducted in languages other than English

• **List of included articles**

Author and year	Aim	Characteristics
Doneria et al. (2017)	Comparative evaluation of caries status in primary and permanent molars in 7–8-year-old schoolchildren of shimla using caries assessment spectrum and treatment index.	-Cross-sectional study -Caries assessment in primary and permanent molars
Baginsk et al. (2014)	Dental caries in primary and permanent molars in 7-8-year-old schoolchildren evaluated with Caries Assessment Spectrum and Treatment (CAST) index.	-Cross-sectional -Aimed to examine caries in primary and permanent molars
Topaloglu-Ak & Eden (2010)	Caries in primary molars of 6–7-year-old Turkish children as risk indicators for future caries development in permanent molars.	-Cross-sectional -Aim of study is to examine if past caries experience in primary molars can be used as a risk indicator for future caries experience in first permanent molars.
Chen et al. (2003)	Relationship of caries experience between primary teeth and the first permanent molars in 100 children of 6-year-old.	-Cross-sectional -Aimed to evaluate the association of caries between primary molars and first permanent molars.
Wang et al., (2003)	An eight-year longitudinal study for caries status on primary and permanent dentitions in Beijing children	- Case report. - Aim of this study is to evaluate the caries status in primary and permanent dentition.
Li and Wang (2002)	Predicting caries in permanent teeth from caries in primary teeth: an eight-year cohort study.	- Cohort study. - The study aimed to examine the correlation between caries in primary and permanent dentition.
Raadal and Espelid (1992)	Caries prevalence in primary teeth as a predictor of early fissure caries in permanent first molars	-Cross Sectional Study -The aim of this study is to evaluate whether caries in primary molars can be used as a predictor for early

		fissure caries in first permanent molars. Fissure caries in first permanent molars.
--	--	---

- **List of excluded articles with reasons**

Author and date	Aim	Reason for exclusion
Qiang and Zhi (2015)	Caries status of the first permanent molar among 6-7 years old and their correlation to caries in primary molars	Study in Chinese language.

- **Review of literature**

Several studies reported that caries in primary teeth is correlated with caries in permanent teeth. A study by **(Raadal & Espelid, 1992)** aimed to examine the validity of employing the caries experience of primary dentition for predicting early fissure caries in the permanent first molar. 192 children were examined, and after the children were grouped according to their dmft a statistically significant relationship was found between the dmft and the number of intact molars in each individual. It indicated that the dmft index of primary teeth should be used as an indicator for the use of preventive methods for fissure caries in permanent molars.

Similarly, **(Li & Wang, 2002)** mentioned in their eight years cohort study, that aimed to determine if caries in primary dentition can predict caries in the permanent dentition of the same individual, that there were statistically significant associations between caries prevalence in primary and permanent dentition ($p < 0.01$). Children who had caries in their primary teeth had three times higher rate of developing caries in their permanent teeth with the permanent molar at highest risk, this concluded that caries in primary teeth could be used as a risk indicator for predicting caries in the permanent teeth.

Furthermore, an eight-years longitudinal study was conducted by **(Wang et al., 2003)** to determine if the caries status in primary teeth can be used as a risk indicator for predicting caries in permanent teeth. A total of 362 children, 3-4 years old in the baseline study in 1992 were reexamined in 2000 based on WHO criteria and methods, the result of this study found a significant association between the caries prevalence in primary teeth and permanent teeth ($P < 0.01$) and between DMFT(s) and dmft(s) ($P < 0.01$). Children who had caries in their primary

teeth were nearly three times more likely to have caries in their permanent teeth (RR=2.6.95% CI = 1.4-4.7, P<0.001). Therefore, this study concluded clearly that caries in the primary teeth can be used as a risk indicator for caries in permanent teeth.

In addition, **(Chen et al., 2003)** examined a total of 100 school children 6 years old. The caries diagnosis criteria defined by WHO were employed. Fisher's exact test showed that there was association between the caries experience of primary teeth and that of the first permanent molars in those children. The average dmft of primary teeth was in positive correlation with DMFT of the first permanent molars ($r=0.5629$). The results were statistically significant, concluding that the primary tooth caries experience may play an important role in predicting permanent tooth caries.

Moreover, another study aimed to investigate whether the past caries experience in primary dentition can be tested to predict subsequent caries in first permanent molars. Clinical examinations were carried out in a school-based screening. 286 Turkish children aged 6-7 years old were examined and caries in the permanent first molars at the age of 10-11 years was then calculated. Caries experience of the primary dentition (dmft), primary molars (dmft molars), and primary second molars (dmft 2nd molars) showed a statistically significant correlation with caries (DMFT) 4 years later in the permanent first molars. Among the variables, the caries experience of the primary second molars was the most powerful caries predictor **(Topaloglu-Ak & Eden, 2010)**

On the other hand, dental caries in primary and first permanent molars among 7-8 years old school children were evaluated using caries assessment spectrum and treatment (CAST) index. On the contrary to previous studies, this study found weak correlation between caries in primary molars and first permanent molars in the same jaw, while the correlation was found moderate in teeth situated in opposite jaws **(Baginska et al., 2014)**

According to the study performed by **(Doneria et al., 2017)**, caries was assessed in 6.3%-12.3% of permanent molars in contrast to the primary molars, in which carries was near about 50%. The correlation was stronger for first and second deciduous molars for the right side of the mouth than the left side ($r=0.293$ and 0.257 in the maxilla and 0.503 and 0.319 in the mandible [$P<0.001$]), respectively, while correlation for teeth in the opposite jaws was moderate [$r=0.20-0.47$], so it concluded that the correlation between first permanent molars and primary molars regarding the caries status were weak while strongest correlation was present on the right side of the mouth for first and second deciduous molars.

- **Aim of the study**

To investigate the correlation between caries experience in primary molars and first permanent molars, among a group of Egyptian children.

- **PICOS**

(P)Population: Egyptian children aged 6 to 9 years old with present primary molars and erupted first permanent molars

(O) Outcome:

Outcome	Outcome measuring	Outcome measuring unit
Primary Outcome: Caries experience in primary molars.	Numerical	deft index
Secondary outcome: Caries experience in first permanent molars.	Numerical	DMFT index

(S)Study design: Cross sectional study

- **Research question**

Is there a correlation between caries experience in primary molars and in the first permanent molars among a group of Egyptian children?

- **Hypothesis**

This research adopts null hypothesis; it assumes that there is no correlation between caries experience in primary molars and first permanent molars.

- **Participants and methods**

- **Ethics**

- All the procedures will be explained to the parents or guardians prior to the investigation.
- An informed consent will be signed by the parents (**Appendix 1**)
- Study design: cross sectional study design.

- **Setting & Location**

Data for this particular study will be collected from the clinic of Pediatric Dentistry and dental public health Department, Faculty of Dentistry, Cairo University.

- **Participants**

- **Eligibility criteria**

- **Inclusion criteria**

1. Children ages from six to nine years
2. Both sexes.
3. Parent and children cooperation.
4. Healthy children.
5. Children with sound and carious primary molars and erupted all of the first permanent molars.

- **Exclusion criteria**

1. Children age under 6 or more than 9 years.
2. Children had a complex metabolic or medical disorder.
3. Parents that will not sign the consent.
4. Children with missing or unerupted first permanent molars.

➤ **Variables**

To control other confounders for caries, additional independent variables will be considered including:

- Gender.
- Number between siblings.
- Only child.
- Socioeconomic status.
- Oral hygiene.
- Type of toothpaste used.

- **Data and sources measurements**

- **Methods**

- Clinical examination will be carried out while the child is sitting on dental unit, using sterile diagnostic set (mirror and explorer) in daylight. No diagnostic radiographs will be taken.
- A custom-made examination chart will be filled for each child including date, name, age, address, gender, medical history and previous dental treatment. Parents data includes: level of education and oral hygiene level.
- Prior to performing dental examination, the child will be asked to rinse his mouth with tap water and the teeth will be cleaned with sterile cotton.
- The examiner will carefully inspect all surfaces of the teeth, for proper diagnosis, the teeth were dried thoroughly with an air syringe. It will be important to see clearly and to use the air syringe to distinguish readily cervical or interproximal caries.
- All the primary teeth will be evaluated using deft index and permanent teeth will be evaluated using DMF index, both according to WHO criteria.

(WHO, 2003) criteria:

- **Clinical caries lesion shows the following criteria**

- Lesion in pit or fissure, or on a smooth tooth surface with cavitated undermined enamel, or a detectably softened floor or wall.
- Teeth with recurrent dental caries.
- In cases where the crown has been destroyed by caries and only the root is left, the caries is judged to be crown caries.

- **Lesions not considered as clinical dental caries**

- White or chalky spots (early carious lesion).
- Stained enamel pits or fissures without visible cavitation or soft floor or walls during examination by sharp explorer.
- Dark, shiny, hard, pitted areas of enamel in a tooth showing signs of moderate to severe enamel fluorosis.
- Each child and parents will be given two printed sheet translated into Arabic, after the end of the diagnosis, which will include his/her caries status, the right oral hygiene method to be followed in order to maintain a good oral health status and any caries

lesions that need treatment by restorative material or preventive measures (**Appendix 4**).

- **Bias**

Possible bias that can occur:

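### Exclusion 4 removes children who lost a first permanent molar to caries, so the M of the first-molar DMFT is zero by construction

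*Protocol*

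**What the plan says.** Five places in the protocol bear on this.

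- **Exclusion criteria, item 4** bars "Children with missing or unerupted first permanent molars". It does not say why the tooth is absent.
- **Inclusion criteria, item 5** asks for children with "erupted all of the first permanent molars", and the PICOS population refers to "erupted first permanent molars". Neither mentions a molar that erupted and was later extracted.
- **PICOS, outcome table** lists "Secondary outcome: Caries experience in first permanent molars", measured by DMFT.
- **Data and sources measurements, Methods** says that "permanent teeth will be evaluated using DMF index, both according to WHO criteria". Under the same criteria, when "only the root is left, the caries is judged to be crown caries", so a retained root counts as D.
- **Appendix 1, examination chart** has separate D, M and F fields and a dental history line. The Methods section says the chart also records "medical history and previous dental treatment".

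The Statement of the problem gives early extraction or root canal treatment of first permanent molars as a main clinical scenario behind the study. It gives no frequency.

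**The concern.** The M in DMFT counts teeth lost because of caries. A rule that bars every child with an absent first molar, whatever the cause, sets that component to zero and lets the outcome decide who is enrolled. A child whose molar is reduced to a root stays in the study and is scored as carious. Once the same molar is extracted, the child is out.

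Among children whose first molars have all erupted, only those with first-molar caries experience can be lost through caries extraction. Mean first-molar DMFT is therefore pulled down. One of the two correlated variables also loses some of its most severe cases, which may weaken the correlation that the study sets out to measure. An analysis plan cannot repair this, because the children are never enrolled. The Bias section relies on including every child who meets the criteria, and here the criteria themselves cause the loss.

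**Working it through.** **Textual check (no assumption needed).** For each child, first-molar DMFT = D + M + F over four teeth. M ≥ 1 requires at least one absent first molar, and exclusion 4 removes every child with one. So M = 0 and DMFT = D + F for every enrolled child. This holds for the first molars only; other permanent teeth could still contribute M to a whole-mouth DMFT.

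**Size (illustrative).** The protocol states no figure to reproduce, so the effect was simulated with 1,000,000 children per setting.

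*Inputs*
- Cited rates (Review of literature): 6.3% and 12.3% of permanent molars and about 50% of primary molars carious. They come from 7-8-year-old schoolchildren scored with a different index (List of included articles), so they are not estimates for this clinic.
- Assumed higher clinic rates: 25% and 40% of first molars.
- Assumed share q of affected first molars already extracted: 2%, 5%, 20%.
- Assumed child-level frailties for primary and permanent molars: correlated logit-normal, SD 1.8, latent correlation 0.5 and 0.7; 8 primary and 4 first permanent molars per child.
- Extraction probability: equal for all affected molars, or clustered (odds ×2.7 per SD of permanent-molar frailty, same average q).

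*Calculation.* Drop children with M ≥ 1, then recompute mean DMFT and the Spearman correlation r. As a rough check, for small q the share dropped is about q × 4 × rate. At q = 5% and a 12.3% rate this is 0.05 × 4 × 0.123 = 2.5%, against 2.4% simulated.

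| q | Setting | Children dropped | Fall in mean DMFT | Fall in r |
|---|---|---|---|---|
| 2% | cited rates | 0.5-1.0% | 3% | 0.003-0.005 |
| 2% | clinic rates | 2-3% | 2.5-3% | 0.002-0.005 |
| 2% | clustered, all four rates | – | 3-4% | 0.006-0.012 |
| 5% | cited rates | 1.2-2.4% | 7-8% | 0.008-0.013 |
| 5% | clinic rates | 5-8% | 6-7% | 0.005-0.013 |
| 5% | clustered, all four rates | – | 8-10% | 0.014-0.028 |
| 20% | cited rates | 4.7-8.9% | 28-29% | 0.03-0.054 |
| 20% | clinic rates | 17-27% | 25-29% | 0.03-0.056 |
| 20% | clustered, all four rates | – | 28-31% | 0.05-0.09 |

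Baseline r was 0.23-0.39 at the cited rates and 0.33-0.50 at the assumed clinic rates.

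*Worked cases at q = 5%, latent correlation 0.7*
- 12.3% rate, equal probability: mean 0.494 to 0.455, a fall of 0.039/0.494 = 7.9%; r 0.394 to 0.380.
- 12.3% rate, clustered: mean 0.494 to 0.446, a fall of 0.048/0.494 = 9.7%; r 0.394 to 0.371.
- 40% rate, equal probability: mean 1.599 to 1.500, a fall of 0.099/1.599 = 6.2%; r 0.502 to 0.495.

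*Against sampling error.* The Sample size calculation section gives no N, so N = 200 is assumed. With SE(r) = (1 − r²)/√(N − 1), the SE is (1 − 0.23²)/√199 = 0.067 at r = 0.23 and (1 − 0.39²)/√199 = 0.060 at r = 0.39. At q = 5% the shift in r is 0.1-0.2 SE, or 0.2-0.5 SE if clustered. At q = 20% it is about 0.5-1.0 SE, or 0.7-1.75 SE if clustered.

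*Sensitivity.* With frailty SD from 1.2 to 2.5 and equal probability, mean DMFT falls by 5-9% and r by 0.004-0.016 at q = 5%. At q = 20% the falls are 21-34% and 0.02-0.07. r moved toward zero in every setting tried.

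**The case against.** The strongest reply is that the restriction may be deliberate. PICOS, inclusion 5 and exclusion 4 can be read together as defining children whose study teeth are all present, and a DMFT with M = 0 is still a valid count. That reading is possible, but the protocol does not state it, and a tooth that has erupted is not necessarily still present. If it is what the sponsor intends, the outcome label and the population to which the result applies should say so.

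Second, the aim, research question and hypothesis concern the correlation, not mean DMFT, and the effect on r is small if extraction is rare. This stands and is the main reason the point is minor. First-molar DMFT is nevertheless a listed outcome that will be reported.

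Third, nothing in the protocol supports q = 20% at ages 6 to 9, and N = 200 is also assumed. This stands: the 20% rows show a range and are not evidence of impact. The consistent direction for r also depends on the settings chosen. Extraction was driven only by permanent-molar caries, and none of the settings let it depend on access to care.

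Fourth, the M field proves little, because the chart covers all permanent teeth. That is fair, but the conclusion follows from exclusion 4 and the stated outcome without it.

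**Conclusion.** The concern holds and is minor. Exclusion 4 as written forces first-molar M to zero and removes children because of their outcome, and no other part of the protocol corrects this. That conclusion rests on the text alone.

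The size does not: it depends on an extraction share that the protocol does not give. With 2-5% of affected molars extracted, mean first-molar DMFT is understated by roughly 2.5-8% (up to 10% if clustered). The correlation falls by at most 0.013 (0.028 if clustered), which is well within sampling error at an assumed N of 200. A higher caries rate mainly raises the share of children lost, with little change in the fall in r or in the relative fall in mean DMFT. The clearer harm is to mean DMFT and to the stated meaning of the outcome.

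**What to change.** Choose one of two options.

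1. **Keep DMFT.** Reword exclusion 4 to: any first permanent molar unerupted, congenitally absent, or lost for a reason other than caries. Align inclusion 5 and the PICOS population to: all first permanent molars erupted, including any later extracted because of caries. Score a first molar as M when the dental history shows extraction for caries. If the history does not show this, exclude the child as now. The rule that "No diagnostic radiographs will be taken" can then stand.
2. **Keep the restriction.** State the outcome as D+F in children with all four first permanent molars present, and limit the conclusions to that group.

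Under either option, report the number of children excluded under item 4 by reason, so that readers can judge the loss.

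The cost is three eligibility sentences under option 1, or one outcome line under option 2. The chart already holds the history and the M field, so no new examination is needed. The drawback of option 1 is that a few M scores rest on dental history or parental recall, and unrecorded caries extractions stay excluded. It therefore reduces the selection but does not remove it entirely.

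### Age is missing from the list of confounders to control, although children aged 6 to 9 are analysed together and age is on every chart

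*Protocol*

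**What the plan says.** Under Participants and methods, the Variables section states a purpose and gives a list: "To control other confounders for caries, additional independent variables will be considered including" gender, number between siblings, only child, socioeconomic status, oral hygiene and type of toothpaste. Age is not among the six.

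The PICOS population is "Egyptian children aged 6 to 9 years old with present primary molars and erupted first permanent molars". The exclusion criteria remove "Children age under 6 or more than 9 years", and inclusion criterion 5 asks for "Children with sound and carious primary molars and erupted all of the first permanent molars". No age strata, quotas or subgroups are described, and the Bias section says that every eligible child is included.

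Age is recorded for every child (Data and sources measurements, Methods; Appendix 1, examination chart). The Statistical methods section names only the software, so nothing else in the protocol brings age into the analysis. The sample size is left to a committee.

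The introduction ties first-molar caries to age and eruption: "At the age of 6 years, occlusal surfaces of the permanent first molars are particularly vulnerable to caries development".

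**The concern.** The sole aim is the correlation between caries experience in primary molars (deft) and in first permanent molars (DMFT), measured at one examination. DMFT is cumulative, and an older child's first molars have usually been exposed for longer. Primary-molar deft can also move with age: up as lesions accrue, or down as primary molars are shed. Criterion 5 applies its word for completeness only to the first permanent molars, so a child who has lost some primary molars is not clearly excluded.

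If both indices move with age, children of mixed ages show a correlation even when none exists among children of the same age. If they move in opposite directions, a real correlation is diluted. Adjusting for gender, family variables, oral hygiene and toothpaste does not remove this. At stake are the test of the null hypothesis of no correlation and the comparison with published coefficients from narrower age bands. One cited study "examined a total of 100 school children 6 years old"; another is titled "Comparative evaluation of caries status in primary and permanent molars in 7–8-year-old schoolchildren of shimla".

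**Working it through.** The protocol states no correlation, sample size or age trend, so there is no figure to reproduce. Two illustrations give the scale.

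**1. Partial-correlation identity.** Let a = corr(age, deft), b = corr(age, DMFT) and p = the correlation at fixed age. The unadjusted correlation is

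r = p × √((1 − a²)(1 − b²)) + a × b.

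With p = 0 this is r = a × b. The values of a and b below are assumptions.

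- a = ±0.2, b = 0.2: r = ±0.04
- a = ±0.4, b = 0.2: r = ±0.08
- a = ±0.4, b = 0.4: r = ±0.16
- p = 0.3, a = ±0.4, b = 0.4: r = 0.3 × 0.84 ± 0.16 = 0.252 ± 0.16, that is 0.09 or 0.41

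By Fisher's z, a purely age-induced r of 0.04, 0.08 or 0.16 is significant at two-sided 5% in about 9%, 20% or 62% of studies with 200 children.

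**2. Simulation on the tooth-count scale.** The only anchor in the protocol is the Review of literature for ages 7 to 8: "caries was assessed in 6.3%-12.3% of permanent molars in contrast to the primary molars, in which carries was near about 50" per cent. Everything else is assumed:

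- Age is uniform from 6.0 to 9.0 or from 6.0 to 9.99, because the upper limit can be read either way.
- Counts are binomial out of 8 primary and 4 first permanent molars, with normal child effects of SD 1.5 on the logit scale.
- First-molar prevalence rises from 5% to 15%, or from 3% to 20%, between ages 6 and 9. This gives about 11% or 12% at ages 7 to 8, inside the cited range.
- Primary-molar prevalence changes by 10 or 30 points around 50%, up or down.
- Trends are logit-linear and extrapolated beyond age 9.
- Spearman correlations come from 600,000 children per scenario. Rejection rates come from 2,000 studies per scenario, with a simulation standard error of at most √(0.25/2000) = 1.1 points.

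Each range covers both first-molar trends. The last column also covers both directions of the primary trend.

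| Upper age | Primary trend | Unadjusted r, absolute value, no association within age | 5% test rejects, n=200 | n=400 | Unadjusted r when the within-age r is about 0.19 |
|---|---|---|---|---|---|
| 9.0 | 10 points | 0.015–0.025 | 5–6% | 6–8% | 0.15–0.20 |
| 9.0 | 30 points | 0.042–0.070 | 9–17% | 13–30% | 0.10–0.24 |
| 9.99 | 10 points | 0.028–0.044 | 6–10% | 8–15% | 0.14–0.23 |
| 9.99 | 30 points | 0.076–0.128 | 19–45% | 31–73% | 0.04–0.30 |

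With no association within age, a flat primary trend gives 0.00. The correlation partialled for age is 0.00 throughout and rejects in 4–6% of studies. Where a true association exists, the age-partial value stays at 0.18–0.20.

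**3. Adjusting for the list but not for age.** Take one covariate of the listed kind, unrelated to age, that affects both dentitions (standard normal, coefficient 0.75 on both logits, total SD kept at 1.5), and no other association. Adjusting for it alone leaves an absolute r of 0.01–0.06 (10-point trends) or 0.04–0.15 (30-point trends). Adding age brings it to 0.00–0.01.

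**4. Narrower age bands.** The same null model gives at most 0.01 among 6-year-olds and 0.01–0.04 at ages 7 to 8.

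**The case against.** The list is introduced as open, no model is stated, and covariate sets are commonly left to a statistical analysis plan, so the harm arises only if the list is treated as complete. That is true, and the conclusion is limited accordingly. But the protocol chose to name confounders for control, and an analyst who follows that list adjusts for toothpaste and not for age.

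Age is also partly handled by design, through the age limits and the requirement that all first permanent molars be erupted. The lead-in could be read as covering confounders beyond those already restricted by eligibility. Restriction narrows the problem, but a range of three years or more remains.

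The points about size are the strongest and largely stand. No age trend comes from the documents, and the introduction gives no rate of increase from 6 to 9. With ages to 9.0 and 10-point trends, the test stays near its nominal level. The largest values need the steep primary trend, the steeper first-molar trend and extrapolation to 9.99 all at once; first-molar prevalence then reaches 32% and primary-molar prevalence 74% or 26%.

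The negative direction is less secure. The population wording on present primary molars may limit shedding, and the simulation does not model shedding; it keeps eight primary molars and lowers the prevalence per tooth. Finally, the cited studies of 7-to-8-year-olds report tooth- and jaw-level correlations on a different index, so their coefficients give scale only.

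**Conclusion.** The concern holds as a conditional statement: a deft-DMFT correlation adjusted only for the six named variables stays open to confounding by age. Size and direction are unknown, because they rest on age trends and a sample size that the protocol does not give. Under mild assumed trends the effect is a few hundredths, small beside cited coefficients of 0.20 to 0.56. Under steep trends it reaches 0.13 with no adjustment and 0.15 after adjusting for a listed-type covariate alone, which is enough to matter if the true correlation is weak. The weight is minor to moderate. It is worth correcting because the correlation is the study's only aim and the remedy costs almost nothing.

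**What to change.** Add age at examination to the Variables list. Report the age-adjusted association beside the unadjusted correlation: either a partial Spearman correlation given age, or a regression of first-molar DMFT on primary-molar deft with age and the listed variables. Interpret the unadjusted figure in the light of the adjusted one, and settle this before the data are analysed. The cost is one line of text and one degree of freedom; age is already on the examination chart, so no new data are needed.
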